#### **Protocol Summary**

Protocol MNEMONIC and Title: RERTEP - A Phase II Trial of Surgery and

Fractionated Re-irradiation for Recurrent Ependymoma

Principal Investigator: [name], DO, PhD

**IND Holder:** C-methionine, IND 104987, Sponsor of IND: St. Jude Children's Research Hospital

**Brief Overview:** There is a need to determine the role of re-irradiation in patients with recurrent ependymoma after prior therapy that includes fractionated radiation therapy administered with curative intent. Outcomes reported from St. Jude Children's Research Hospital suggest that a proportion of children with recurrent ependymoma after prior irradiation may be successfully treated with additional surgery and a second course of irradiation; however, there are a number of unanswered questions about this approach including portability, morbidity and mortality, and the biological basis for success. Responding to these questions requires prospective study of outcomes and tumor biology.

Intervention: Neurosurgery and fractionated irradiation.

Rev. 3.2 dated: 1/19/2023

Protocol document date: 1/19/2023

Brief Outline of Treatment Plan: The goal of this study is to determine the feasibility and safety of treating recurrent ependymoma with a second course of irradiation using cumulative doses that exceed those used in routine clinical practice. Surgery is an important part of this study and will be used to document recurrent ependymoma and reduce the tumor burden when feasible. Patients with local failure after prior surgery and focal irradiation will undergo surgery and focal re-irradiation; however, those age > 3 years with tumors having 1q gain will be offered craniospinal irradiation. Those with metastatic disease limited to the neuraxis will receive craniospinal irradiation after surgery. Patients with combined local and distant failure will be treated with surgery and craniospinal irradiation. Patients will be stratified for outcome according to diagnosis and prior therapy. All patients will be evaluated for the effects of the treatment regimen.

St. Jude Children's Research Hospital IRB NUMBER: Pro00004349 IRB APPROVAL DATE: 02/01/2023

#### Primary Objective:

1.1 To estimate the progression-free and overall survival distributions for children and young adults with recurrent ependymoma treated with a second course of irradiation while monitoring for excessive central nervous system necrosis.

Responsible Investigator: [name] Biostatistician: [name] and [name]

**Estimated date for completion of data collection**: 10-11 years after activation.

### **Secondary and Exploratory Objectives:**

1.2 To explore potential associations of clinical and treatment factors with the incidence and severity of neurological, endocrine and cognitive deficits in children and young adults with ependymoma treated with a second course of irradiation.

Responsible Investigators: [name] and [name]

Biostatisticians: [name] and [name]

Estimated date for completion of data collection: 10-11 years after activation.

1.3 Using specific measures of sleep quality, excessive daytime sleepiness, daytime activity, fatigue, symptom distress, and quality of life, explore associations of sleep, fatigue and quality of life with other measures of CNS effects, clinical and treatment factors in children and young adults with ependymoma treated with a second course of irradiation.

Responsible Investigator: [name]

Biostatisticians: [name]

Estimated date for completion of data collection: 10-11 years after activation.

1.4 To describe physical performance and movement in children, adolescents and young adults with ependymoma treated with a second course of irradiation.

**Responsible Investigator: [name]** 

Biostatisticians: [name]

**Estimated date for completion of data collection**: 10-11 years after activation.

1.5 Estimate and compare the response of recurrent tumor and the incidence and severity of macrostructural, microstructural, physiologic and vascular effects on brain tissue in children and young adults with ependymoma after treatment with a second course of irradiation using specific methods of diffusion, contrast-enhancement, magnetization transfer, vascular neuroimaging, and explore the association between these and other measures of CNS effects and clinical and treatment factors.

Responsible Investigators: [name] and [name]

St. Jude Children's Research Hospital IRB NUMBER: Pro00004349

Biostatisticians: [name]

**Estimated date for completion of data collection:** 10-11 years after activation.

1.6 Estimate the avidity of ependymoma to F-fluorodeoxyglucose (FDG) and C-methionine positron emission tomography (IND # 104987) prior to radiation therapy and correlate change in avidity 12, 24 and 36 months after a second course of irradiation with tumor progression.

Responsible Investigator: [name]

Biostatisticians: [name]

Estimated date for completion of data collection: 10-11 years after activation.

1.7 Measure growth factor and cytokine responses in children and young adults with ependymoma after treatment with a second course of irradiation, and explore associations between these and other measures of CNS effects and clinical and treatment factors. Descriptively compare findings to similar growth factors and cytokines evaluated in historic patients during their initial course of irradiation.

Responsible Investigator: [name]

Biostatistician: [name]

Estimated date for completion of data collection: 10-11 years after activation.

1.8 Conduct molecular analyses on tumor samples (and blood where a germline control is required) with the aim of studying associations between tumor molecular subgroup and treatment response and various side effects, including vasculopathy, hearing loss, cognitive deficits, growth hormone deficiency, and other measures as appropriate.

Responsible Investigator: [name]

Biostatistician: [name]

Estimated date for completion of data collection: 10-11 years after activation.

1.9 To explore the association of chemotherapy given prior to re-irradiation with PFS and OS distributions.

#### **Hypotheses:**

1.1.1 Hypothesis for Primary Objective – Ependymoma recurrent after prior therapy that included irradiation is genetically distinct from the untreated tumor. The effectiveness of a second course of irradiation depends on tumor biology and the pattern of initial tumor progression.

St. Jude Children's Research Hospital IRB NUMBER: Pro00004349 IRB APPROVAL DATE: 02/01/2023

IRB Approval date:

Hypothesis for Secondary Objective - A second course of irradiation may be safely administered to patients with recurrent ependymoma after prior irradiation. The incidence and severity of side effects after second irradiation correlate with relevant clinical factors and treatment parameters, including radiation dose to normal tissue volumes. The selection of patients for re-irradiation can be improved by models that include clinical and treatment factors and longitudinal measures of CNS effects.

Criteria for Evaluation: Disease control will be evaluated using MR imaging performed during regular intervals after enrollment. Patients will be considered to have progressive disease when there is progressive growth of any component of the tumor based on serial imaging.

Study Design: Phase II study assessing the rate of failure for patients with ependymoma treated with surgery and a second course of irradiation.

#### **Inclusion Criteria:**

- 1. Progressive intracranial ependymoma after prior focal irradiation
- 2. Patients aged 1-21 years at the time of enrollment
- 3. Adequate performance status (ECOG < 3) and research participant does not require mechanical ventilation
- 4. Interval from start of initial radiation therapy to enrollment > 9 months

#### **Exclusion Criteria:**

- 1. Prior craniospinal irradiation
- 2. Pregnant women are excluded from this study because radiation therapy is an agent with the potential for teratogenic or abortifacient effects.
- 3. Any patient with both metastatic ependymoma and age <3 years at the time of enrollment

Sample Size: Accounting for ineligible patients, the total number of patients to be accrued to this study is estimated to be 99. We expect to enroll about 12 patients per year for a period of 8-9 years.

Randomization: N/A

## **Data Analyses: Primary Aim:**

To estimate the progression-free and overall survival distributions for children and young adults with recurrent ependymoma treated with a second course of irradiation while monitoring for excessive central nervous system necrosis.

#### **Secondary Aims:**

Evaluate functional outcomes and host and tumor biology in patients with recurrent ependymoma treated with a second course of irradiation.

**Primary Anticipated Completion Date:** May, 2023

**Anticipated Study Completion Date:** May, 2028

**Timeframe for Primary Outcome Measure:** Five years after last patient has been enrolled.

Rev. 3.2 dated: 1/19/2023 Protocol document date: 1/19/2023

St. Jude Children's Research Hospital IRB NUMBER: Pro00004349

**Data Management:** Data management will be provided by the clinical research staff in the Department of Radiation Oncology at St. Jude Children's Research Hospital and all data will be entered and maintained in the St. Jude CRIS database.

**Human Subjects:** The risks to subjects treated with surgery and re-irradiation are expected to be higher when compared to initial surgery and radiation therapy. Patients previously treated with surgery and radiation therapy have accepted the burden of risk associated with those treatments including neurological, endocrine, cognitive and somatic dysfunction. We estimate that these risks will be magnified depending on whether the volume for the second course of irradiation is limited to the primary tumor bed or craniospinal. The effects of craniospinal irradiation are known to be largely dependent on age at the time of treatment. Regardless of treatment approach, the short term side effects may include nausea, vomiting, fatigue, loss of appetite, hair loss and headache. Common late effects include hormone deficiencies and weight gain, fatigue and sleep disorders, cognitive effects (memory, attention, behavior, learning, global intelligence), headache and permanent hair loss. Less common late effects are secondary tumor formation (benign or malignant), vasculopathy and stroke, neurological effects such as hearing loss, vision loss and seizures, and structural effects such as necrosis or myelopathy that may lead to permanent disability or death. Patients will be informed of this and other possible side effects during informed consent. Adverse events will be monitored, reported, and treated appropriately. The risks to subjects may be increased from surgery include all of the side effects listed above in addition to delayed wound healing, infection and stroke. The use of chemotherapy at any time may increase the side effects of re-irradiation.

Rev. 3.2 dated: 1/19/2023

Protocol document date: 1/19/2023

#### 1.1 Primary Hypothesis and Objective

Hypothesis: Ependymoma recurrent after prior therapy that included irradiation is genetically distinct from the untreated tumor. The effectiveness of a second course of irradiation depends on tumor biology and the pattern of initial tumor progression.

1.1.1 To prospectively estimate the progression-free and overall survival distributions for children and young adults with recurrent ependymoma treated with a second course of irradiation while monitoring for excessive central nervous system necrosis.

#### 1.2 Secondary Hypotheses and Secondary Objectives

Hypotheses: A second course of irradiation may be safely administered to patients with recurrent ependymoma after prior irradiation. The incidence and severity of side effects after second irradiation correlate with relevant clinical factors and treatment parameters, including radiation dose to normal tissue volumes and the use of chemotherapy before or after second irradiation. The selection of patients for re-irradiation can be improved by models that include clinical and treatment factors and longitudinal measures of CNS effects.

- 1.2.1 To explore potential associations of clinical and treatment factors with the incidence and severity of neurological, endocrine and cognitive deficits in children and young adults with ependymoma treated with a second course of irradiation
- 1.2.2 Using specific measures of sleep quality, excessive daytime sleepiness, daytime activity, fatigue, symptom distress, and quality of life, explore associations of sleep, fatigue and quality of life with other measures of CNS effects, clinical and treatment factors in children and young adults with ependymoma treated with a second course of irradiation.
- 1.2.3 To evaluate and explore differences in physical performance and movement in children and young adults with ependymoma treated with a second course of irradiation.
- 1.2.4 Estimate and compare the response of residual tumor and the incidence and severity of structural, physiological, and vascular effects of normal brain in children and young adults with ependymoma after treatment with a second course of irradiation using specific methods of diffusion, contrast-enhancement, magnetization transfer, vascular and functional

Rev. 3.2 dated: 1/19/2023 IRB Approval date: Protocol document date: 1/19/2023

St. Jude Children's Research Hospital

IRB NUMBER: Pro00004349

neuroimaging, and explore the association between these and other measures of CNS effects and clinical and treatment factors. Determine the time course of gray matter and white matter tract injury and recovery post irradiation and the association between imaging metrics derived from serial quantitative neural imaging and radiation dosimetry as well as neuro-cognitive outcomes.

#### 1.3 **Exploratory Objectives**

- Estimate the avidity of ependymoma to F-fluorodeoxyglucose (FDG) 1.3.1 and C-methionine positron emission tomography (IND # 104987) prior to radiation therapy and correlate change in avidity 12, 24 and 36 months after a second course of irradiation with tumor progression.
- 1.3.2 Measure growth factor and cytokine responses in children and young adults with ependymoma after treatment with a second course of irradiation, and explore associations between these and other measures of CNS effects and clinical and treatment factors. Descriptively compare findings for patients treated with an initial course of irradiation.
- 1 3 3 To conduct a variety of exploratory molecular analyses on tumor samples (and blood where a germline control is required), including but not limited to broad (genome-wide / array-based) or focused (gene-specific) analyses at the DNA, RNA, or protein level and next generation (whole genome, exome, transcriptome) sequencing in an effort to improve our understanding of ependymoma biology, and to explore associations between molecular findings and treatment response and various side effects including vasculopathy, hearing loss, cognitive deficits, and growth hormone deficiency and other measures as appropriate.
- To explore the association of chemotherapy given prior to re-irradiation 1.3.4 with progression-free survival and overall survival distributions.
- 1 3 5 To compare the progression-free and overall survival distributions for children (age > 3 years) and young adults with recurrent ependymoma and 1q gain treated with a second course of irradiation (focal or craniospinal) while monitoring for excessive central nervous system necrosis.

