To minimize the risks to the patient, there should be a 9-month interval between the start of the first course of radiation therapy and the start of the second course. The rational for this eligibility inclusion criteria including avoiding treatment of patients who have not passed the usual time period after the initial course of radiation therapy when necrosis might begin to appear and increasing the time interval between the start of the first course of radiation therapy and the second course, a known factor to precipitate necrosis. Brainstem radiation necrosis after the initial course of radiation therapy usually occurs within 6 months of completing radiation therapy or less than 8 months after the start of irradiation [6]. We would not want to initiate a second course of treatment for a patient that has

IRB Approval date: St. Jude Children's Research Hospital

not passed this phase. Because the follow-up of children with ependymoma may vary between 3 and 4 months, it is reasonable to be conservative and specify an interval of 9 months. Further, patients who experience necrosis after a second course of irradiation appear to have a higher risk when the interval from first to second RT course is shorter than 6 months. This has been documented in two series [9, 17]. Fortunately, tumor progression during the first year after the initial course of radiation therapy is uncommon.

Patients treated with a second course of irradiation at St. Jude have not been systematically evaluated for late effects. Among the 23 patients who had not failed salvage therapy, we observed that 4 had notable disabilities. The remaining patients continue to be followed and the magnitude of side effects has been greatest among those treated with craniospinal irradiation. Given the very small volume that is targeted for focal fractionated re-irradiation, barring structure damage to the brainstem, the risks of endocrinopathy, hearing loss and cognitive decline do not appear to be significantly greater that that observed after the initial treatment course.

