### **Stopping Rule for Necrosis:**

Necrosis will be monitored throughout the trial and accrual to the trial suspended at any time the following stopping criteria are met. Necrosis will be graded according to the CTCAE v4.0 terminology. If evidence develops that more than 20% of patients are expected to develop necrosis (CTCAE v4.0 > grade 3) the treatment will be considered unacceptable. The number of patients who experience necrosis is based upon the number of enrolled patients. The stopping criteria shown in the following table are based on exact lower 95% Blyth-Still-Casella confidence bounds.

> St. Jude Children's Research Hospital IRB NUMBER: Pro00004349

IRB Approval date: IRB APPROVAL DATE: 02/01/2023

Number of Patients	Number of Eligible	Exact 95% Lower
Experiencing Necrosis	Patients	Confidence Bounds
7	≤ 20	≥ 0.201
10	≤ 30	≥ 0.193
13	≤ 40	≥ 0.204
16	≤ 50	≥ 0.211
18	≤ 60	$\geq$ 0.204
20	≤ 70	≥ 0.202
23	≤ 80	≥ 0.211

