So, the 1q gain status is important factor to consider when plan treatment of cranial spinal irradiation vs. focal irradiation by historic data. We will offer patients the optional second course of cranial spinal irradiation treatment when they have 1q gain in this procol. We will compare PFS and OS of patients with 1q gain status who receive cranial spinal irradiation vs. focal irradiation by log rank test if sample size is reasonable big. Due to the expected limited sample sizes, the results of these exploratory analyses will be considered as descriptive.

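### The only necrosis stopping rule pools focal and craniospinal patients, so a rate well above the 20% limit in one group can fail to trigger it

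*Combined protocol and SAP*

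**What the plan says.** Section 11.1 (Stopping Rule for Necrosis) sets the limit: where "more than 20% of patients are expected to develop necrosis (CTCAE v4.0 > grade 3) the treatment will be considered unacceptable". On the denominator it states that "The number of patients who experience necrosis is based upon the number of enrolled patients". The boundary is 7 cases in up to 20 patients, 10 in 30, 13 in 40, 16 in 50, 18 in 60, 20 in 70 and 23 in 80. These limits "are based on exact lower 95% Blyth-Still-Casella" confidence bounds. Neither the text nor the table separates focal from craniospinal patients, or one stratum from another.

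Section 7.0 gives a single anticipated range for necrosis at one year, above 5% and below 20%, for all patients.

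On volume, the Human Subjects paragraph of the Protocol Summary says of the treatment: "these risks will be magnified depending on whether the volume for the second course of irradiation is limited to the primary tumor bed". The alternative it names is the craniospinal volume. Section 2.1 reports that "the magnitude of side effects has been greatest among those treated with craniospinal irradiation".

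Objective 1.3.5 covers 1q-gain patients "treated with a second course of irradiation (focal or craniospinal) while monitoring for excessive central nervous system necrosis". Its analysis in section 11.10 reads "We will compare PFS and OS of patients with 1q gain status who receive cranial spinal irradiation vs. focal irradiation by log rank test", and that section describes no necrosis summary.

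**The concern.** Focal and craniospinal re-irradiation are different treatments given to different patients. Under section 4.3 (Stratum 4), some patients who would otherwise be treated focally may choose the craniospinal volume. A rule that counts everyone together protects the average patient. If the two groups differ, the lower-risk group dilutes the higher-risk one, whichever that is, and accrual to the worse group can continue at a rate the plan itself calls unacceptable. Because necrosis monitoring is part of the primary objective, the boundary should be able to respond to an excess in either treatment.

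**Working it through.** **1. The printed table.** The bounds behave as the lower limit of a 90% two-sided exact interval, that is, a one-sided 95% bound. Shortest exact acceptance regions give 0.2015, 0.2025 and 0.211 for 7/20, 20/70 and 23/80 (printed 0.201, 0.202, 0.211). For 10/30, 13/40, 16/50 and 18/60 the printed 0.193, 0.204, 0.211 and 0.204 lie within about 0.001 of the one-sided Clopper-Pearson values 0.1933, 0.2041, 0.2121 and 0.2037. The table is reproduced.

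**2. Inputs.**
- Patients: 90 eligible (section 3.3). The table ends at 80, so the pooled rule cannot trigger after patient 80.
- Split: none is planned, and section 4.3 sets no limit per stratum. Table 11.0 gives 22/50 = 44% treated focally. If all local failures were treated focally, the share would be (22 + 7)/50 = 58%. I use 44%, 50% and 58%.
- Necrosis rates: none are given by volume. I assume 40% (twice the limit) in one group and 5%, 10% or 20% in the other. The 5% and 20% are the ends of the section 7.0 range.
- Each limit is applied after every patient and outcomes are taken as known at once. Patients enrolled without enough follow-up would slow both the pooled and the by-group rule.

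**3. The dilution.** Pooled rate = f × focal rate + (1 − f) × craniospinal rate, where f is the focal share. With 5% focal and 40% craniospinal:
- f = 0.44: 0.022 + 0.224 = 24.6%
- f = 0.50: 0.025 + 0.200 = 22.5%
- f = 0.58: 0.029 + 0.168 = 19.7%

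The pooled rate therefore sits close to the 20% limit while one group is at twice that limit.

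**4. Probability of a trigger, craniospinal rate 40%** (40,000 simulated trials per setting; an exact binomial recursion of the pooled rule to 80 patients agrees to within about one percentage point):

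| Focal rate | Pooled rule, focal share 44 / 50 / 58% |
|---|---|
| 5% | 41 / 27 / 14% |
| 10% | 56 / 43 / 28% |
| 20% | 83 / 77 / 67% |

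The printed table applied to craniospinal patients alone triggers in 94 / 92 / 89%.

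**5. Roles reversed (focal 40%).** With craniospinal at 5%, the pooled rule triggers in 17 / 28 / 46% at focal shares of 44 / 50 / 58%. The table applied to focal patients alone triggers in 90 / 92 / 94%.

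**6. Price of adding the by-group counts to the pooled count** (any of the three crossing, same true rate in both groups):

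| True rate | Pooled only | Pooled plus by group |
|---|---|---|
| 20% | about 15% | about 26% |
| 15% | about 3% | about 7% |
| 10% | about 0.3% | about 0.7% |

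**7. Small subsets.** With 11 patients at a true 40%, the printed table triggers with probability about 0.10; with 8 patients, about 0.01. A boundary for Stratum 4 or for 1q-gain patients would offer almost no protection.

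**The case against.** **Volume and necrosis.** A reader might infer that the protocol expects necrosis to differ by volume. It does not say so. The Human Subjects sentence refers back to neurological, endocrine, cognitive and somatic dysfunction, and section 2.1 speaks of side effects in general. Section 7.0 gives one necrosis range for everyone. Elsewhere section 2.1 ties necrosis concern to infratentorial location and to a short interval between courses. It also reports a higher median combined dose for focal patients (111.6 Gy) than at craniospinal overlap (99 Gy). The absence of necrosis in 13 focal patients settles little: the one-sided 95% upper bound is 1 − 0.05^(1/13) = 20.6%. This stands. The point rests on two different treatments sharing one boundary with no volume-specific rate, not on a known direction of risk.

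**Visibility.** A reader might infer that a 40% rate would go unnoticed. It would not. Section 9.3 sends cumulative grade 3–5 summaries to the IRB. Section 11.2 reports grade 3–5 neurological toxicity, compares severity between the two treatment arms, and sends an interim analysis to the CT-SRC once 15 patients per stratum have a year of follow-up. What remains is that neither route carries a stopping boundary. Section 9.1.2.1 also lists necrosis among events not treated as serious or unexpected.

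**Scenario.** No document supports 40% against 5%. At 58% focal the pooled rate is 19.7%, and a rule about the overall rate is right not to stop there. If the other group is at 20%, the pooled rule triggers in most trials. This is why a range is shown.

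**Objective 1.3.5.** A reader might take it as promising a necrosis comparison of focal with craniospinal treatment. Its clause repeats the primary objective's wording, which the trial-wide rule can serve, and section 11.10 calls its own analysis descriptive. The gap there is only the missing summary.

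**Conclusion.** The concern holds as a limitation of the rule in section 11.1: its single pooled count can miss a rate well above 20% in one treatment group. With 40% in the craniospinal group and 44–58% focal patients, the chance that no boundary is crossed is 59–86% if the focal rate is 5%, 44–72% if it is 10%, and 17–33% if it is 20%. By-group use of the same table reduces this to about 6–11%. The result is similar if focal treatment carries the higher risk. The split and the group rates are assumptions, because the documents give neither. The documents do not support saying that such a rate would be invisible, or that the protocol predicts more necrosis after craniospinal treatment.

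**What to change.** In section 11.1, state that the printed table is applied to the pooled count and also separately to patients given focal and patients given craniospinal re-irradiation, classified by treatment received. A group crossing suspends accrual to that group pending review. In section 11.10, report necrosis counts with exact intervals by volume for Stratum 4 and 1q-gain patients, without a boundary.

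This takes about one sentence in each section, with no new data and no new threshold. The cost is more suspensions at the limit itself (about 15% to 26% at a true 20% in both groups). At lower rates the increase is small in absolute terms, as shown above, and a crossing suspends accrual for review rather than ending the trial.
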